10.31 Special Situations for Expedited Reporting

Exceptions to Expedited Reporting: EXPECTED Serious Adverse Events

An expedited report or notification form may not be required for specific Grade 1, 2, 3 and 4 Serious Adverse Events where the AE is **EXPECTED**. Any protocol specific reporting procedures MUST BE SPECIFIED BELOW and will supersede the standard Expedited Adverse Event Reporting Requirements (Note: These adverse events must still be reported through the routine reporting mechanism [i.e. Nadir/adverse events form]; see footnote 1):

System Organ Class (SOC)	Adverse event/Symptoms	CTCAE Grade at which the event will not be expeditedly reported.
General disorders and administrations site conditions	Fatigue	Grade 3
Investigations	Malaise	
	White blood cell decreased	
	Platelet count decreased	Grade 3 and Grade 4
	Neutrophil count decreased	
Blood and lymphatic system disorders	Anemia	Grade 3 and Grade 4

1. These exceptions only apply if the adverse event does not result in hospitalization. If the adverse event results in hospitalization, then the standard expedited adverse events reporting requirements must be followed.

Specific protocol exceptions to expedited reporting should be reported expeditiously by investigators **ONLY** if they exceed the expected grade of the event, except in the event of a hospitalization (follow reporting instructions for section 10.4).

10.311 Persistent or Significant Disabilities/Incapacities

Any AE that results in persistent or significant incapacity or substantial

disruption of the ability to conduct normal life functions (formerly referred to as disabilities), congenital abnormalities or birth defects, must be reported immediately if they occur at any time following treatment with an agent under an IND/IDE since they are considered to be a serious AE and must be reported to the sponsor as specified in 21 CFR 312.64(b).

10.312 Death

- Any death occurring within 30 days of the last dose, regardless of attribution to an agent/intervention under an IND/IDE requires expedited reporting within 24-hours.
- Any death occurring greater than 30 days with an attribution of possible, probable, or definite to an agent/intervention under an NCI IND/IDE requires expedited reporting within 24-hours.
- **Reportable categories of Death**
 - Death attributable to a CTCAE term.
 - Death Neonatal: A disorder characterized by cessation of life during the first 28 days of life.

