13.0 Treatment/Follow-up Decision at Evaluation of Patient

- 13.1 Patients who are without progression will continue treatment per protocol.
- 13.2 Patients who develop PD while receiving therapy will go to the event-monitoring phase.
- 13.3 Patients who go off protocol treatment for reasons other than PD will go to the event-monitoring phase per Section 18.0.
- 13.4 A patient is deemed *ineligible* if after registration, it is determined that at the time of registration, the patient did not satisfy each and every eligibility criteria for study entry. The patient will go directly to the event-monitoring phase of the study (or off study, if applicable).
 - If the patient received treatment, all data up until the point of confirmation of ineligibility must be submitted. Event monitoring will be required per Section 18.0 of the protocol.
 - If the patient never received treatment, on-study material and the end of active treatment/cancel notification form must be submitted. No further data submission is necessary.
- 13.5 A patient is deemed a *major violation*, if protocol requirements regarding treatment in cycle 1 of the initial therapy are severely violated that evaluability for primary end point is questionable. All data up until the point of confirmation of a major violation must be submitted. The patient will go directly to the event-monitoring phase of the study. Event monitoring will be required per Section 18.0 of the protocol.
- 13.6 A patient is deemed a *cancel* if he/she is removed from the study for any reason before any study treatment is given. On-study material and the End of Active Treatment/Cancel Notification Form must be submitted. No further data submission is necessary.

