
Serious adverse events that have been reported with this class of drugs include suicide attempt, suicidal ideation, severe depression, relapse of drug addiction/overdose, nerve palsy (facial, oculomotor), cardiomyopathy, myocardial infarction, retinal ischemia, retinal vein thrombosis, transient ischemic attack, supraventricular arrhythmias, loss of consciousness, neutropenia, infection (pneumonia, abscess), autoimmune thrombocytopenia, hyperthyroidism, rheumatoid arthritis, interstitial nephritis, lupus-like syndrome, aggravated psoriasis and urticaria.

15.18 Drug procurement: Drug is supplied by PharmaEssentia and provided free of charge to study subjects.

15.19 Nursing Guidelines:

15.191 Patients may experience injection site reactions including pain, erythema.

15.192 Monitor LFT's, report increases to the study team.

15.193 Monitor CBC w/diff. Leukopenia and neutropenia have been seen with agent.

15.194 Patients may experience fever. Treat symptomatically and monitor for effectiveness.

15.195 Arthralgias, and back pain were common. Treat symptomatically and monitor for effectiveness.

15.196 Given the similarity between this agent and pegylated IFN, patients may experience similar reactions and side effects. Carefully review those with patients based on the published data for pegylated IFN. Additionally this information is found in section 15.17 of the protocol.

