16.33 Exploratory & Correlative Endpoints (Both Cohorts)

16.331 Patient-reported outcomes: Patient-reported outcomes will be an exploratory component of this trial. Patient-reported symptoms and quality of life (QOL) will be described at each time point using the mean, confidence interval, median, and range. The MPN-SAF will be analyzed using published scoring algorithms. For the MPN-SAF, we will investigate changes in individual symptoms, changes in a symptom scale composed of symptoms specific to MF patients (night sweats, itching, abdominal discomfort, abdominal pain, early satiety, and bone pain) similar to the subset of symptoms used in the COMFORT clinical trials, and changes in the MPN Total Symptom Score (MPN-TSS, Emanuel et al, J Clin Oncol 2012 [in press]). Interpretation will take into consideration that the MPN-TSS includes symptoms potentially irrelevant to this MF population. Graphical procedures will include stream plots of individual patient scores and plots of average values over time. Correlational analyses will be done to determine the relationships among patients-reported symptoms and QOL, as well as with clinical outcomes (best overall response and overall survival) and clinician-assessed symptoms (NCI CTCAE v4). Such correlations will be done at single data time points.

16.4 Data & Safety Monitoring:

16.41 The study chair(s) and the study statistician will review the study at least twice a year to identify accrual, adverse event, and any endpoint problems that might be developing. The Mayo Clinic Cancer Center (MCCC) Data Safety Monitoring Board (DSMB) is responsible for reviewing accrual and safety data for this trial at least twice a year, based on reports provided by the MCCC Statistical Office.

16.42 Adverse Event Stopping Rules: The stopping rules specified below are based on the knowledge available at study development. The stopping rule applies to the

overall study, regardless of cohort. We note that the Adverse Event Stopping Rule may be adjusted in the event of either (1) the study re-opening to accrual or (2) at any time during the conduct of the trial and in consideration of newly acquired information regarding the adverse event profile of the treatment(s) under investigation. The study team may choose to suspend accrual because of unexpected adverse event profiles that have not crossed the specified rule below.

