Accrual will be temporarily suspended to this study if at any time we observe events considered at least possibly related to study treatment (i.e. an adverse event with attribute specified as “possible”, “probable”, or “definite”) that satisfy the following:

- if 2 or more patients in the first 6 treated patients in either cohort (or 30% after the first 6 treated patients have been accrued) experience a grade 4 or higher non-hematologic adverse event.

We note that we will review grade 4 and 5 adverse events deemed “unrelated” or “unlikely to be related”, to verify their attribution and to monitor the emergence of a previously unrecognized treatment-related adverse event.

16.5 Results Reporting on ClinicalTrials.gov: At study activation, this study will have been registered within the “ClinicalTrials.gov” website. The Primary and Secondary Endpoints (i.e., “Outcome Measures”) along with other required information for this study will be reported on ClinicalTrials.gov. For purposes of timing of the Results Reporting, the initial estimated completion date for the Primary Endpoint of this study is 19 months after the study opens to accrual. The definition of “Primary Endpoint Completion Date” (PECD) for this study is at the time the last patient registered has completed treatment.

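### The only event-triggered study-level safety rule requires no pause after a single treatment-related death, never counts a related death coded as hematologic, and has no effect once enrolment has closed

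*Combined protocol and SAP*

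**What the plan says.** Section 16.42 sets one quantitative safety boundary. It opens: "Accrual will be temporarily suspended to this study if at any time we observe events considered at least possibly related to study treatment". The early limit applies "if 2 or more patients in the first 6 treated patients in either cohort" have a qualifying event. Beyond that point the limit becomes a proportion, given in brackets as "or 30% after the first 6 treated patients have been accrued". Under both limits, the patients who count are those who "experience a grade 4 or higher non-hematologic adverse event". The same section says that the rule applies to the "overall study, regardless of cohort".

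Four features follow from the text:

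- **Events counted.** Only non-hematologic events of grade 4 or 5 with at least possible attribution count. There is no hematologic limb and no separate limb for grade 5.
- **Action.** The only consequence is a temporary suspension of accrual.
- **Duration.** Section 16.23 expects Stage 1 accrual to last 19 months and the Stage 1 analysis to begin at about month 25. Section 13.1 says: "Patients who are without progression will continue treatment per protocol". The test schedule in 4.0 runs past cycle 12, with visits every three cycles.
- **Known toxicity.** The nursing guidelines in 15.19 state: "Leukopenia and neutropenia have been seen with agent". Section 15.17 lists neutropenia and thrombocytopenia among the common laboratory effects of marketed pegylated interferon.

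Other provisions also bear on safety:

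- one recruitment pause, with safety review, after the first 3 cohort 2 patients (16.211);
- optional suspension by the study team, and a check of the attribution of grade 4–5 events called unrelated (16.42);
- study-team and DSMB review at least twice a year (16.41);
- 24-hour reporting of deaths (10.312);
- routine submission of grade 3–4 events whatever their attribution (10.522);
- patient-level dose modification (Section 8).

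**The concern.** Section 1.3 says that P1101 has not been studied in myelofibrosis, so a death attributed to the drug would be important information. A pre-set rule is there to guarantee a pause and an independent look, so that neither depends on a judgement made at the time. As written, this rule gives no such guarantee in three situations:

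1. A single related non-hematologic death.
2. Any number of related deaths coded as hematologic, for a drug whose named laboratory risks include cytopenias.
3. Any crossing of the threshold after enrolment closes, because suspending accrual then has no meaning.

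The stake is that enrolment, or continued treatment of patients already in the trial, could go on after a related death without a required study-level look at the data. At about 1 patient per month (16.23), roughly 6 patients could enter between two DSMB reviews six months apart.

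**Working it through.** **No figure to reproduce.** The documents give no operating characteristics for the 16.42 rule.

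**Inputs.** The thresholds and qualifying event come from 16.42. The Stage 1 maximum is 19 patients, 13 in cohort 2 and 6 in cohort 1 (16.22). The related-death rate p is an assumption: 5%, with a range of 2% to 10%.

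**Step 1: patients needed to meet the rule.** For n ≤ 6 the number is 2. For n > 6 it is the smallest integer at or above 0.30 × n.

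| Treated patients n | 0.30 × n | Patients needed |
|---|---|---|
| up to 6 | – | 2 |
| 7–10 | 2.1–3.0 | 3 |
| 11–13 | 3.3–3.9 | 4 |
| 14–16 | 4.2–4.8 | 5 |
| 17–19 | 5.1–5.7 | 6 |

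One related death is below the threshold at every n. The requirement is lightest in the first six and rises to 6 patients by full enrolment.

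**Step 2: chance of at least one related death in 19 patients**, 1 − (1 − p)^19:

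- p = 2%: 1 − 0.98^19 = 0.319
- p = 5%: 1 − 0.95^19 = 0.623
- p = 10%: 1 − 0.90^19 = 0.865

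**Step 3: chance that the current rule requires a pause.** This step takes the case most favourable to the rule on coding: every related death is non-hematologic. It also supposes that no other grade 4 event qualifies. In the first six patients the chance is 1 − (1 − p)^6 − 6p(1 − p)^5. At p = 5% this is 1 − 0.7351 − 0.2321 = 0.033. An exact binomial recursion then applies the Step 1 thresholds after each further patient, up to n = 19 pooled over cohorts.

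| Assumed p | At least one related death in 19 | Pause required, pooled | Death(s) but no required pause |
|---|---|---|---|
| 2% | 31.9% | 0.6% | 31.3% |
| 5% | 62.3% | 3.7% | 58.6% |
| 10% | 86.5% | 14.1% | 72.4% |

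If all such deaths were coded as hematologic, the third column would be 0% at every p.

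**Step 4: does the choice of denominator matter?** If the rule is run separately in each cohort, the chance that either cohort crosses is 1 − (1 − a)(1 − b), where a is for 6 patients and b for 13. At 5%: 1 − (1 − 0.033)(1 − 0.037) = 0.068. At 2%: 1 − (1 − 0.0057)(1 − 0.0060) = 0.012. At 10%: 1 − (1 − 0.114)(1 − 0.139) = 0.237. The chance is higher than when pooled, but still far below the chance of a related death. The text does not settle which reading applies.

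**Step 5: after enrolment.** With accrual planned to end at month 19 and analysis at about month 25, at least 25 − 19 = 6 months of follow-up fall after the rule's only action has lapsed. Section 13.1 lets treatment run on without a fixed end.

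**The case against.** The plan is not without protection. 16.211 mandates a recruitment pause after three cohort 2 patients, with no event count and no restriction to non-hematologic toxicity. Deaths within 30 days of the last dose, and later ones that are at least possibly related, need reporting within 24 hours. White cells, neutrophils and platelets are graded at every evaluation (10.51), and grade 3–4 events are submitted routinely. The study team may suspend accrual at any time. DSMB review and the dose modifications in Section 8 do not stop when accrual closes, and a Stage 2 amendment could reopen accrual. Cytopenias are also part of the disease (1.1), so leaving them out of a count-based trigger is an understandable choice. All of this stands.

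It also rules out several stronger readings that a reader might infer:

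- *That 16.42 is the only pre-set safety provision.* It is not, given 16.211. It is the only event-triggered rule at study level.
- *That hematologic deaths escape expedited reporting.* The exemption in 10.31 covers listed grade 3–4 events, and "These exceptions only apply if the adverse event does not result in hospitalization". Deaths are not exempt.
- *That late class effects would mostly appear after accrual closes, or that most patients would then still be on drug.* The documents give no onset times and no retention figures.
- *That many deaths would probably pass unremarked.* Step 1 allows up to 3 of 13 or 5 of 19 qualifying patients without a crossing, but only if the events accumulate late enough to stay below every earlier threshold. At a 5% rate, exactly 5 deaths in 19 has probability of about 0.2%.

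What the objection does not supply is a required study-level response to a related death. Each safeguard is discretionary, one-off, calendar-based, limited to reporting or confined to the individual patient.

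**Conclusion.** The point holds in this limited form. Section 16.42 pools death with grade 4 toxicity, excludes hematologic events and acts only on accrual. A lone related death therefore never requires a pause, a related death coded as hematologic never counts, and a crossing after enrolment closes requires nothing. The threshold counts follow directly from the text.

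The probabilities (62% against about 4% at a 5% rate; 32–86% against 0.6–14% across 2–10%) are illustrative. They rest on an assumed death rate, independent patients, each outcome being known before the next patient is counted, a pooled denominator, and no other qualifying grade 4 events. Other qualifying events would make the rule fire more often; hematologic coding would make it fire less often. A death following cytopenia might be coded as infection or bleeding and would then count, so the single-death gap is the firmest part of the point.

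This is a gap in guaranteed response. It does not show that deaths would go unseen. It should be corrected because the change is small and the drug is new to this disease.

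**What to change.** Amend 16.42 in three places:

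1. Any grade 5 event at least possibly related to P1101, hematologic or not, suspends accrual pending DSMB review.
2. Meeting either this criterion or the existing threshold, whether or not accrual is open, triggers an expedited DSMB review that covers patients still on treatment.
3. Reconcile "overall study, regardless of cohort" with "if 2 or more patients in the first 6 treated patients in either cohort", and state whether the count of six and the 30% use pooled or cohort-specific denominators.

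These changes leave dosing and individual treatment decisions untouched. The cost is a few sentences. The downside is a possible short accrual pause and an unscheduled review by a board that already exists.

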16.6 Inclusion of Women and Minorities

16.61 This study will be available to all eligible patients, regardless of race, gender, or ethnic origin.

16.62 There is no information currently available regarding differential effects of this regimen in subsets defined by race, gender, or ethnicity, and there is no reason to expect such differences to exist. Therefore, although the planned analysis will, as always, look for differences in treatment effect based on racial and gender groupings, the sample size is not increased in order to provide additional power for subset analyses.

16.63 The geographical region served by this study, has a population which includes approximately 7% minorities. Based on prior MMC studies involving similar disease sites, we expect about 7% of patients will be classified as minorities by race and about 33% of patients will be women. Expected sizes of racial by gender subsets for patients registered to this study are shown in the following table:

Accrual Estimates by Gender/Ethnicity/Race

Ethnic Category	Sex/Gender			
	Females	Males	Unknown	Total
Hispanic or Latino	0	1		1
Not Hispanic or Latino	6	12		18
Ethnic Category: Total of all subjects*	6	13		19
Racial Category				
American Indian or Alaska Native	0	0		0
Asian	0	0		0
Black or African American	0	1		1
Native Hawaiian or other Pacific Islander	0	0		0
White	6	12		18
Racial Category: Total of all subjects*	6	13		19

Ethnic Categories: **Hispanic or Latino** – a person of Cuban, Mexican, Puerto Rico, South or Central American, or other Spanish culture or origin, regardless of race. The term “Spanish origin” can also be used in addition to “Hispanic or Latino.”
Not Hispanic or Latino

Racial Categories: **American Indian or Alaska Native** – a person having origins in any of the original peoples of North, Central, or South America, and who maintains tribal affiliations or community attachment.
Asian – a person having origins in any of the original peoples of the Far East, Southeast Asia, or the Indian subcontinent including, for example, Cambodia, China, India, Japan, Korea, Malaysia, Pakistan, the Philippine Islands, Thailand, and Vietnam. (Note: Individuals from the Philippine Islands have been recorded as Pacific Islanders in previous data collection strategies.)
Black or African American – a person having origins in any of the black racial groups of Africa. Terms such as “Haitian” or “Negro” can be used in addition to “Black or African American.”
Native Hawaiian or other Pacific Islander – a person having origins in any of the original peoples of Hawaii, Guam, Samoa, or other Pacific Islands.
White – a person having origins in any of the original peoples of Europe, the Middle East, or North Africa.

17.0 Pathology Considerations/Tissue Biospecimens

None

18.0 Records and Data Collection Procedures

18.1 Submission Timetables

Initial Material(s) -

Case Report Form (CRF)	Active-Monitoring Phase (Compliance with Test Schedule Section 4.0)
On-Study	
Adverse Event - Baseline	
Measurement - Baseline	
Bone Marrow and Cytogenetics	
Bone Marrow Biopsy Report including Cytogenetics	≤2 weeks after registration
JAK2V617F, BCR/ABL, CALR AND MPL	
Research Blood Submission	
End of Active Treatment/Cancel Notification	Submit ≤2 weeks after registration if withdrawal/refusal occurs prior to beginning protocol therapy
Patient Questionnaire	≤2 weeks after registration – Patient questionnaire booklet must be used; copies are not acceptable for this submission.
Booklet Compliance	≤2 weeks after registration – This form must be completed only if the [name of booklet(s) – or whatever verbiage you want to use to describe the booklet(s)] contains absolutely NO patient provided assessment information.

Test Schedule Material(s)

CRF	Active-Monitoring Phase (Compliance with Test Schedule Section 4.0)	
	At each evaluation during treatment	At end of treatment
Evaluation/Treatment	X	X
Concurrent Transfusion	X	X
Interval Laboratory	X	X
Bone Marrow and Cytogenetics	X ³	
Bone Marrow Biopsy Report including Cytogenetics	X ³	
JAK2V617F, BCR/ABL, CALR AND MPL	X	
Nadir/Adverse Event	X	X
Measurement	X	X
Research Blood Submission	X (see Section 14.0)	
Patient Questionnaire	X ¹	
Booklet Compliance	X ²	
End of Active Treatment/Cancel Notification		X
ADR/AER	At each occurrence (see Section 10.0)	

1. Patient questionnaire booklet **must** be used; copies are not acceptable for this submission.
2. This form must be completed **only** if the booklet contains absolutely **NO** patient provided assessment information.
3. Only required when bone marrow biopsy is performed.

Follow-up Material(s)

CRF	Event Monitoring Phase ¹				
	q. 3 months until PD and/or subsequent treatment ²	At PD ²	After PD and/or subsequent treatment q. 6 mos.	Death	New Primary
Event Monitoring	X	X	X	X	At each occurrence

1. If a patient is still alive 3 years after registration, no further follow-up is required.
2. Submit copy of documentation of response or progression to the MCCC Operations Office, Attention: QAS

19.0 Budget

- 19.1 Costs charged to patient: routine clinical care
- 19.2 Tests to be research funded: P1101 study drug is supplied by PharmaEssentia and provided free of charge to study subjects.
- 19.3 Other budget concerns: none

